## **D. Data, Study Sample, Outcomes, and Other Variables**

### **D.1. Data and Study Samples**

The study sample will be recruited from the population of eligible households in Monroe, Onondaga, and Westchester counties, New York. We will randomly select 50 households per county into the treatment arm, and 100 households per county into the control arm.

Data will be obtained from two sources:

1) A web-based survey for all study participants at baseline, at 6 months after treatment begins, at 12 months after treatment begins, and at 18 months after treatment begins (6 months after treatment ends). This survey will collect information on caretaker and child demographic, health, behavioral, educational, and social characteristics. All variables will be collected at baseline. We will repeat data collection for all time-varying variables at each post-baseline wave of the survey.

2) OCFS administrative records linked to the study participants and their children using the DOB and name of the study participant and all minor children in the participant's household. Data will be provided by OCFS as family-specific and child-specific counts of a series of events related to child maltreatment reports and agency interventions.

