## Secondary outcomes:

Secondary outcomes are related to child and family health, well-being, and stability. All outcomes are measured during each wave of survey data collection [baseline, 6 months, 12 months, 18 months]. For all measures derived from additive indices, we will treat measures as continuous. If the empirical distributions of additive indices are roughly symmetric, we will treat them as continuous real numbers. If the empirical distributions of additive indices are skewed, we will treat them as non-negative integers.

- Parental self-reported general health (19 physical health items derived from SF-36): items scored following RAND Corporation SF-36 scoring instructions for included questions. Additive index
- Mental health (Kessler 10 plus) Each item is scored from one 'none of the time' to five 'all of the time'. Scores of the 10 items are then summed, yielding a minimum score of 10 and a maximum score of 50. Additive index
- Stress and coping (Perceived Stress Scale - 4): Each item is scored from "never" to "all of the time" on a 5-point scale. Scores of 4 items are then summed, yielding a minimum score of 0 and a highest score of 16. Higher scores are correlated to more stress. Additive index
- Family dynamics and parenting (CHAOS): Each item is scored "yes" or "no". Scores of the items are then summed. The higher the score the higher the level of environmental chaos in the home. Additive index
- Parental Stress Scale: 18-item questionnaire assessing parents' feelings about their parenting role, exploring both positive aspects (e.g. emotional benefits, personal development) and negative aspects of parenthood (e.g. demands on resources, feelings of stress). Each item is scored on a 5-point Likert scale. Parental stress scores range from 18 to 90, with lower scores indicating lower levels of parental stress. Additive index
- Food insecurity: In the past four weeks, did you worry that your household would not have enough food? Binary
- Adult Hope Scale: 12 items scored on an 8-point ordinal scale. Additive index
- Child missed medical care: Parental yes/no report of any child in home with missed medical care in preceding 6 months. Binary
- Child truancy: Parental report of day of missed school for each child in the home aged 6-17 in the preceding 6 months. Ordinal [no missed days; 1-3 days; 4-6 days; 7-10 days; 11 or more days; child not enrolled in school]

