- Hours per week of relative childcare: Parent-reported number of hours each week each child 0-5 spends receiving care from a relative other than a parent or guardian.
- Hours per week of non-relative child care: Parent-reported number of hours each week each child 0-5 spends receiving care from a non-relative. Non-negative continuous
- Hours per week of formal childcare: Parent-reported number of hours each week each child 0-5 spends receiving care in a day care center, preschool, or prekindergarten. Non-negative continuous
- Financial-well being (CFPB Financial Well-Being Scale: Each item is scored 0 to 4 and summed to a total following CFPB scoring instructions. Additive index.
- Housing instability: 3-items counting number of moves, rating home quality, and rating neighborhood quality. Additive index.

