### D.3. Participant Characteristics

We will collect the following demographic and socioeconomic information from participants:

- Age
- Gender
- Self-reported race
- Self-reported ethnicity
- Number of adults in household
- Number of children in household
- Educational attainment
- Monthly income from employment
- Monthly income from other government benefits
- Employment
- Health Insurance Status (Insured versus uninsured)
- Child Health Insurance Status (If any child in home is uninsured)
- Housing status

In the event that there are high levels of missingness for any key covariate (i.e., >2%), multiple imputation methods will be used.

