### **E.2. Statistical specification**

Our primary analytic approach is an analysis based on the intent-to-treat principle that compares outcomes for those randomized into the treatment group to those who were randomized into the control group.

Our models account for time-stable heterogeneity across individuals and treatment sites using random intercepts for each individual enrolled in the study, for each time period during which surveys are collected, and for the county from which their qualifying OCFS case originated. These random effects adjust for correlation induced by repeated measurements of individuals over time, time period effects, and clustering of outcomes within counties.

Our regression models for outcome variable  $y$  take the following general form:

$$\mu = E(y|T, X) = \alpha_i + \delta_j + \gamma_k + \beta T_i + c_j T_i + \theta X_{ij}$$

$$\begin{pmatrix} \alpha \\ \delta \\ \gamma \end{pmatrix} \sim N(0, \Sigma)$$

Where  $T$  indicates selection into the treatment group,  $X$  is a matrix of demographic characteristics,  $i$  indicates an individual participant,  $k$  indicates county of residence at the time of study enrollment,  $j$  indicates survey time period,  $\alpha$  is a vector of individual-level intercepts,  $\delta$  is a vector of time period intercepts,  $\gamma$  is a vector of county-level intercepts,  $\beta$  is the time-stable component of the treatment effect,  $c$  is a vector of time-varying components of the treatment effect, and  $\theta$  is a vector of coefficients for demographic predictors.

The relationship between the treatment and outcomes of interest may vary as a function of time. We treat temporal relationships as potentially nonlinear, and model the relationship between time, treatment, and outcomes of interest using a series of time-period intercepts. We estimate a unique intercept for each treatment period as well as an interaction between treatment status and treatment period to capture time-varying effects of treatment.

For all continuous (additive index) outcomes with a roughly symmetric distribution, we treat the outcome as following a linear model where

$$y \sim N(\mu, \sigma^2)$$

For all binary outcomes, we treat the outcome as following a Bernoulli model

$$y \sim \text{Bernoulli}(p)$$

$$E(p|T, X) = \text{logit}^{-1}(\mu)$$

And for all count outcomes and additive index outcome with a non-symmetric distribution, we treat the outcome as following a negative binomial model

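### Secondary survey outcomes only: the E.2 model, as written, makes little or no use of the baseline score that the trial already collects; adjusting for it is a free gain in precision, of uncertain size

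*Combined protocol and SAP*

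**What the plan says.** **Baseline data.** Section D.1 says of the survey: "All variables will be collected at baseline". Section D.2 says of the secondary outcomes: "All outcomes are measured during each wave of survey data collection [baseline, 6 months, 12 months, 18 months".

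**Covariates.** In Section E.2, X "is a matrix of demographic characteristics" and θ "is a vector of coefficients for demographic predictors". The list in Section D.3, introduced by "We will collect the following demographic and socioeconomic information from participants", contains no outcome score.

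**Treatment terms.** The E.2 equation contains βT_i + c_jT_i. T marks selection into the treatment group and j indexes the survey time period, so the arm difference at wave j is β + c_j. No constraint is given for the baseline wave. The prose describes an "interaction between treatment status and treatment period to capture time-varying effects of treatment".

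**Effect measure.** E.2 defines the average treatment effect (ATE) as a difference in expected outcome level between arms. It does not say whether the baseline wave is included.

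**Other uses of baseline.** Section E.1 uses baseline characteristics to check balance and attrition. Section E.4 re-estimates the same models with informative priors. Neither adjusts for the baseline outcome.

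**The concern.** A participant's baseline score is usually among the best predictors of the later score. In a randomised comparison, using it narrows the interval for the arm difference at no data cost. With 150 treated and 300 control households, 14 survey outcomes and a multiplicity adjustment (Section E.5), precision matters here.

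It is easy to assume that the participant random intercept already does this job. It does not when the arm difference is also free at baseline: the baseline rows are then used up in estimating a separate baseline contrast.

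The silence on baseline rows also leaves open, at analysis time, whether baseline enters as an outcome row and whether the reported effect averages over it.

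**Working it through.** The plan states no power, SD or correlation, so there is no figure of its own to reproduce beyond the allocation: 3 × 50 = 150 and 3 × 100 = 300.

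**Inputs.** From the documents: 150 versus 300, and four waves. Assumed: a continuous participant-level outcome with unit SD; correlation r equal between all waves, or decaying as 0.5, 0.4 and 0.3 at lags of 6, 12 and 18 months; X explaining R² of the variance, all of it between persons.

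**Formulas.** S is the 4 × 4 covariance matrix, P its post-baseline block, b the covariances with baseline, s₀₀ the baseline variance and w = (1/3, 1/3, 1/3). The variance of the arm difference is (1/150 + 1/300) = 0.01 times a factor:
- without baseline: w′Pw
- with baseline: w′(P − bb′/s₀₀)w
- to allow for X, subtract R² from every entry of S.

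**Step 1: does the written model use baseline?** Generalised least squares with complete data gives these SEs for the three-wave mean:

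| Assumption | Post-baseline rows only | Four waves, arm difference free | Four waves, common baseline mean |
|---|---|---|---|
| r = 0.5 | 0.0816 | 0.0816 | 0.0645 |
| Decay | 0.0803 | 0.0803 | 0.0696 |

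The first two columns agree. In 100 simulated trials at r = 0.5, the 18-month estimate from the free model equalled the raw difference in means to within 8 × 10⁻¹⁵.

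Two features let baseline add a little. With an assumed 20% monotone dropout and r = 0.5, the relative 18-month variance is 0.972 without baseline rows, 0.941 with them and 0.741 with a common baseline mean. Shrinking the random period effects gives at most about 2%.

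**Step 2: what would using baseline gain for the three-wave mean?**

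| r | R² | Without | With | Cut |
|---|---|---|---|---|
| 0.3 | 0 | 0.533 | 0.443 | 17% |
| 0.3 | 0.1 | 0.433 | 0.389 | 10% |
| 0.3 | 0.2 | 0.333 | 0.321 | 4% |
| 0.5 | 0 | 0.667 | 0.417 | 38% |
| 0.5 | 0.1 | 0.567 | 0.389 | 31% |
| 0.5 | 0.2 | 0.467 | 0.354 | 24% |
| 0.7 | 0 | 0.800 | 0.310 | 61% |
| Decay | 0 | 0.644 | 0.484 | 25% |
| Decay | 0.1 | 0.544 | 0.444 | 18% |
| Decay | 0.2 | 0.444 | 0.394 | 11% |

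With assumed retention of 90%, 80% and 70%, decay and R² = 0.2, the SE goes from 0.0728 to 0.0693, a variance cut of 1 − (0.0693/0.0728)² ≈ 9%.

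**Step 3: 18 months alone.** Before allowing for X, the cut is r²: 9%, 25% and 49% at r = 0.3, 0.5 and 0.7. With decay it is 5% at R² = 0.1 (0.900 to 0.856) and 2% at R² = 0.2 (0.800 to 0.788). If the plan's single random intercept is fitted to decaying correlations with R² = 0.2, a common baseline mean gives an 11% cut for the three-wave mean but about a 1% loss at 18 months.

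**Step 4: change from baseline.** Reporting the same fit as change does not recover the gain. The three-wave factors are 0.933, 0.667 and 0.400 at r = 0.3, 0.5 and 0.7 (R² = 0), against 0.443, 0.417 and 0.310 with adjustment.

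**The case against.** **The plan may already do this.** Its prose interacts treatment with treatment period, and no treatment effect can exist before treatment. If the treatment terms are zero at baseline, the gain is already in the plan. This reading is possible and cannot be excluded. It does not fit the stated definitions, though: T_i has no period index and means selection into the treatment group, and j is the survey period. If it is what the sponsor intends, one sentence would settle it.

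**The remedy needs a baseline unaffected by assignment.** Section C places the baseline survey only before treatment starts. It does not say that the survey precedes randomisation or notification of arm. Answers on stress, hope or finances could shift once a family knows its arm, and forcing equal baseline means could then bias the contrast. This objection stands, and the fix is conditional on it.

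**The gain is assumed, and can be small.** This also stands. No correlation, R² or retention figure is in the documents. The calculation covers continuous outcomes only; two of the 14 outcomes are binary, truancy is ordinal, and skewed indices move to a negative binomial model.

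**Stronger readings that the documents do not support.** A reader might infer that omitting the baseline score biases the planned comparisons. It does not: the contrast between randomised arms is valid without it. A reader might also infer that the main results lose precision. The primary outcomes are administrative events counted from baseline to 18 months and have no baseline survey score, so they are outside this point. Nor do the documents support a fixed sample-size equivalent: 1/(1 − cut) runs from about 1.04 to 1.60 across the 4% and 38% cases alone.

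**Conclusion.** The point holds as an efficiency improvement for the secondary survey outcomes. As the E.2 equation is written, the baseline score adds no precision to the post-baseline contrasts with complete data and freely estimated period effects, and only a little otherwise.

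For continuous outcomes, the three-wave variance would fall by roughly 4% to 38% across r = 0.3 to 0.5, and by 61% at r = 0.7 with X explaining nothing. With decaying correlations and X explaining 20%, the figure is about 11%, or 9% with dropout. A benefit at 18 months alone should not be promised. Gains for binary, ordinal and negative binomial outcomes are not quantified.

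The change is worth making because the data are already planned and it also settles how baseline rows enter the model. That second benefit does not depend on any assumed correlation.

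**What to change.** 1. **Confirm timing.** State whether the baseline survey is completed before participants learn their arm. The steps below assume that it is; if it is not, option (b) should not be used.
2. **Ten participant-level outcomes.** Choose one option, not both: (a) model the 6-, 12- and 18-month values with the baseline value of the same outcome added to X; or (b) keep baseline rows in y and set the arm difference at baseline to zero.
3. **Four per-child measures.** These are truancy ("Parental report of day of missed school for each child in the home aged 6-17 in the preceding 6 months") and the three childcare-hours items (for example "Parent-reported number of hours each week each child 0-5 spends receiving care from a relative other than a parent or guardian"). Use (b) throughout. Children can enter the age range, be born or join the household after baseline, and (b) accepts a child with no baseline value. Do not mix (a) and (b) within one outcome.
4. **ATE.** State that for survey outcomes it is a post-baseline contrast that excludes the baseline wave. Fix the wave or average before analysis and report each wave. For logit and negative binomial outcomes, average the ATE over the sample, because adjustment changes the conditional coefficient.
5. **Missing baseline scores.** If (a) is used, say that the Section D.3 imputation rule covers the baseline score.

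The cost is SAP wording and slightly more programming for the averaged ATE. No extra data or participants are needed.

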### E.3. Subgroup analyses

Families involved with OCFS have varying levels of exposure to structural racism. Because of this we expect that treatment effects may vary as a function of participant race/ethnicity. We examine possible treatment heterogeneity by modifying our general regression model as follows:

$$\mu = E(y|T, X) = \alpha_i + \delta_j + \gamma_k + d_l(\beta T_i + c_j T_i) + \theta X_{ij}$$

where  $d$  is an interaction coefficient for participant race  $l$  on both the time-stable and time-varying components of the treatment effect.

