### **D.2. Planned Outcomes**

#### **Primary Outcomes:**

Primary outcomes are measured as event counts between baseline and 18 months after the beginning of study interventions using OCFS administrative data. We will treat all primary outcome events as integer count variables, with the exception of preventive services which will be treated as binary (services delivered / no services delivered). In the event that observed study outcomes are rare in the sample, we will treat primary outcomes as binary (occurred / did not occur) instead of treating rare outcomes as event counts.

The primary study outcomes (and variable class) are:

- Investigative Track OCFS maltreatment cases: event count
- Family Assessment Response (FAR) track OCFS cases: event count
- Total OCFS cases: event count as sum of investigative track and FAR track cases
- Indicated OCFS maltreatment investigations: event count
- Substantiated OCFS maltreatment investigations: event count
- OCFS foster care placements: event count
- Preventive services for families at risk of foster care: binary

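### The race/ethnicity subgroup formula leaves d without a scale or sign and forces every group's effects over time to be proportional

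*Combined protocol and SAP*

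**What the plan says.** The general model in section E.2 has the treatment and covariate terms "\beta T_i + c_j T_i + \theta X_{ij". There beta "is the time-stable component of the treatment effect", and the c_j supply "an interaction between treatment status and treatment period to capture time-varying effects of treatment". Only the individual, period and county intercepts are given a distribution; beta and c are free.

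Section E.3 expects effects to vary by race/ethnicity and modifies the model by placing a multiplier in front of the whole treatment term: "d_l(\beta T_i + c_j T_i" (the closing bracket follows). It says that d "is an interaction coefficient for participant race $l$ on both the time-stable and time-varying components of the treatment effect". It states no reference group, no fixed value or sum constraint, no distribution for d, and no test of heterogeneity.

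Two kinds of outcome go through this model. For the secondary outcomes, section D.2 says "All outcomes are measured during each wave of survey data collection", that is, at baseline and at 6, 12 and 18 months. For the administrative outcomes it says "Primary outcomes are measured as event counts between baseline and 18 months after the beginning of study interventions", which gives one record per family.

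**The concern.** Read as printed, the group-l effect in period j is the product `d_l × (beta + c_j)`. This raises three problems.

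- **Identification.** A product of two free factors does not determine either factor. An analyst cannot fit or report d without a choice that the plan does not make. The usual null for an interaction coefficient, d = 0, would here mean no treatment effect in that group. Absence of heterogeneity is equality of the d_l.
- **Proportionality.** E.2 allows the effect to change freely over time. E.3 then lets the groups differ only by a constant multiple of one time profile. With 12 months of payments and a survey 6 months after they end, groups could well differ in when an effect appears or fades.
- **Testing.** When the treatment effect is null or weak, the common profile is barely determined. The fit can then choose the profile along which the groups happen to differ most, so a standard test of equal d_l rejects too often.

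This is the plan's only subgroup analysis. The Benjamini-Hochberg step in section E.5 cannot repair p-values that are invalid before adjustment.

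**Working it through.** The plan gives no figure on this point to reproduce. The number of race/ethnicity groups, L, is not stated, so it is varied. The number of periods, J, is 3 for the post-baseline waves, 4 if baseline is included, and 1 for the primary outcomes.

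**1. Scale and sign.** For any non-zero k, `(k d_l) × ((beta + c_j)/k) = d_l × (beta + c_j)`. Checked with k = 2, −1 and −0.5: the group-by-wave effects are identical.

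**2. Rank.** The treatment part has L + 1 + J parameters (d, beta, c). The rank of the derivatives of the L × J cell effects is L + J − 1.

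| Treatment term | L | J | Parameters | Rank |
|---|---|---|---|---|
| E.2 alone | – | 3 | 4 | 3 |
| E.3 as printed | 4 | 3 | 8 | 6 |
| E.3 with c_ref = 0 | 4 | 3 | 7 | 6 |
| E.3 with c_ref = 0, d_ref = 1 | 4 | 3 | 6 | 6 |
| Additive interactions with references | 4 | 3 | 12 | 12 |

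One of the two deficits comes from E.2, where no reference period separates beta from c. The other belongs to E.3 and remains after the first is removed. The pattern is the same for L = 2 to 6 and J = 1, 3 and 4. If beta + c_j = 0 in every period, the derivatives with respect to d vanish and the data say nothing about d.

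**3. Proportionality.** The normalised E.3 term has 6 free parameters for 12 cell effects (L = 4, J = 3). Suppose the true effects over three waves are (−0.4, −0.4, 0) in one group and (0, −0.2, −0.4) in another. The best proportional fit is (−0.32, −0.40, −0.16) and (−0.16, −0.20, −0.08). At the last wave it reverses the order: the group with no effect is fitted at −0.16, and the group with an effect of −0.4 at −0.08.

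**4. Size of a test of equal d_l.** The test considered is a likelihood-ratio test comparing the best proportional fit with identical rows, referred to chi-square on L − 1 degrees of freedom. Normal cell estimates were simulated 100,000 times at zero treatment effect.

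| J | L = 2 | L = 3 | L = 4 | L = 5 |
|---|---|---|---|---|
| 3 | 0.165 | 0.188 | 0.199 | 0.212 |
| 4 | 0.215 | 0.253 | 0.277 | 0.297 |

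With J = 1 the size is 0.05. With unequal groups (45/30/20/5%), within-person correlation 0.5, L = 4 and J = 3, it is 0.202. The joint test of additive interactions stayed at 0.049 to 0.052 in all runs.

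**5. Dependence on the true effect.** With 150 treated and 300 controls in 4 equal groups and no attrition, each group has 37.5 and 75. The standard error per group and wave is √(1/37.5 + 1/75) = 0.20 SD. For 3 waves, 2 to 5 equal groups and within-person correlation 0 to 0.7, the size is:

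- 0.12 to 0.19 at a common effect of 0.1 SD;
- 0.07 to about 0.14 at 0.2 SD;
- 0.05 to 0.07 at 0.4 SD.

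**The case against.** The strongest reply is that the bracket is shorthand. E.2 is a regression linear in its coefficients, E.3 only modifies it, and the description of d as an interaction "on both the time-stable and time-varying components of the treatment effect" can be read as ordinary race-by-treatment and race-by-treatment-by-period terms. On that reading all three problems disappear and only a notation correction remains. This may be what was meant, but E.3 does not say so. Full interactions need a second coefficient indexed by both group and period, and E.3 has only d_l.

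Other points stand in part:

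- The cell effects `d_l × (beta + c_j)` are identified, as are the ratios of the d_l when the effect is not zero. The treatment effect in E.2 is defined as a difference in expected outcomes, so group contrasts can be reported under any normalisation. This is correct, but those contrasts still carry the proportionality restriction.
- The test sizes are conditional: they need a literal product fit, a test that E.3 does not name, and a null or weak effect. The 4-wave figures also allow a treatment effect at baseline, before payments begin, so 3 waves is the relevant case.
- Informative priors in section E.4 could fix the scale, but only in the Bayesian sensitivity analysis, and none is stated for d.
- The reach is limited to a subgroup analysis, chiefly of the secondary survey outcomes.

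**Conclusion.** The concern holds for the formula as printed. E.3 adds one unidentified direction to the one already in E.2. Once normalised, it still cannot represent group differences in the timing of effect. That conclusion rests on algebra and needs no assumption about group sizes or tests. The restriction acts on the scale of the linear predictor: log for counts, logit for binary outcomes.

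The false-positive figure of 0.16 to 0.21 at zero effect is conditional on 3 waves, 2 to 5 groups and a chi-square test of equal d_l, and it fades as the effect grows.

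For the single-record primary outcomes d still lacks a scale and sign, but proportionality over time does not arise and the test of equal group effects holds its size. The main intent-to-treat comparison is unaffected. This should be corrected before analysis, but it does not threaten the trial's main conclusion.

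**What to change.** Replace the E.3 formula with additive interactions:

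`mu = alpha_i + delta_j + gamma_k + beta T_i + c_j T_i + d_l T_i + e_lj T_i + theta X_ij`

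and state the following.

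- **References.** c_ref = 0 and e_l,ref = 0 for a named period; d_ref = 0 and e_ref,j = 0 for a named race/ethnicity group.
- **Periods.** Use the post-baseline waves. If baseline is kept as a period, multiply every treatment term by a post-baseline indicator so that it is zero at baseline.
- **Covariates.** Put race/ethnicity and race/ethnicity-by-period terms in X. Without the latter, a group drifting by 0.2 SD per wave in both arms, with no treatment effect, produces false e_lj of 0.2 and 0.4 SD. With them the false effect is 0.
- **Test and reporting.** Test d_l and e_lj jointly, once per outcome, and report group-specific effects with confidence intervals.
- **Primary outcomes.** Use beta T_i + d_l T_i only, with the race/ethnicity main effect in X.

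If the printed formula was meant as shorthand for these terms, the same edit settles it.

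The cost is one formula and two or three sentences, with no new data. The price is precision. With 4 equal groups and no attrition, the 95% half-width for one group's effect is 1.96 × 0.20 = 0.39 SD at one wave. Averaged over 3 waves at within-person correlation 0.5 it is 1.96 × 0.20 × √((1 + 2 × 0.5)/3) = 0.32 SD.

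The choice of test also matters. In that same setting, if one group differs by a constant 0.5 SD, power is about 0.40 for the joint test (9 degrees of freedom) against 0.59 for a test on the wave-averaged effect (3 degrees of freedom). The latter also holds its size but is blind to timing. Whichever is chosen should be fixed in advance.

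### The E.3 race-subgroup model has no race-by-wave intercepts, so for repeated survey outcomes a race difference in trend shared by both arms can appear as a race difference in the effect of cash

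*Combined protocol and SAP*

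**What the plan says.** The general model in E.2 has individual, wave and county intercepts, a treatment effect β, wave-specific treatment components c_j, and demographic covariates. On time it states: "We estimate a unique intercept for each treatment period as well as an interaction between treatment status and treatment period". The wave term δ "is a vector of time period intercepts", with no race index. X "is a matrix of demographic characteristics" and θ "is a vector of coefficients for demographic predictors", with no wave index. Race is on the list of collected variables in D.3 ("Self-reported race"), so a race main effect inside θX is plausible, although it is not named. The random intercepts are described thus: "Our models account for time-stable heterogeneity across individuals and treatment sites using random intercepts".

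E.3 changes only the treatment terms, to "d_l(\beta T_i + c_j T_i) + \theta X_{ij". The coefficient d_l for race group l acts "on both the time-stable and time-varying components of the treatment effect". Nothing else in the model becomes race-specific. E.4 re-estimates the same models with informative priors, so no planned sensitivity analysis adds a race-by-wave term either.

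**The concern.** Every d_l term is multiplied by T and so is zero for controls. The control mean for race l at wave j is δ_j plus, at most, a constant for race. The treated families of each race can follow their own path over the waves, but the controls of all races share one path up to a constant shift.

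Randomisation makes the treated families of a race group comparable with the controls of that same group. E.3 compares them instead with a control trend pooled over groups. Suppose one group's stress or food-insecurity answers drift differently over 18 months in both arms, for reasons unrelated to the cash. Only the treated cells have parameters that can absorb the drift, so it is read as effect heterogeneity. In E.2 the plan pairs its treatment-by-wave terms with wave intercepts; E.3 adds race to the former without adding it to the latter.

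E.3 is the only heterogeneity analysis in the plan, and its output is a statement about which racial groups gain from cash. A multiplicity adjustment as in E.5 does not correct a biased contrast.

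**Working it through.** The plan gives no effect size, SD or subgroup figure, so there is no stated result to reproduce.

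**Inputs from the plan.** 150 treated and 300 control families (3 × 50 and 3 × 100; C and D.1); four survey waves at 0, 6, 12 and 18 months (D.1, D.2); two-sided 0.05 (E.5, stated there for the primary outcome).

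**Assumptions not in the plan.** Outcome SD 1; within-person correlation 0.5; two race groups, 60/40, giving 90 and 60 treated and 180 and 120 control families; race main effect in X; free race-by-treatment-by-wave terms; linear model; no attrition; no effect of cash in either group. The second group drifts linearly by D over 18 months, equally in both arms.

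**Bias in the E.3 structure.** The race main effect absorbs the average drift, D/2. The remainder at each wave goes to the treatment-by-race terms. For D = 0.3 the drift is 0, 0.1, 0.2, 0.3 with mean 0.15, so the spurious race differences in effect are −0.15, −0.05, +0.05 and +0.15 SD. Hence:
- 18-month effect: D/2
- change from baseline to 18 months: D
- average over waves: 0

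**Standard errors.** Using all four cells, V = 1/90 + 1/180 + 1/60 + 1/120 = 0.04167. Using treated cells only, V_T = 1/90 + 1/60 = 0.02778.
- Wave average: variance (1 + 3 × 0.5)/4 × V = 0.625 × 0.04167 = 0.02604; SE 0.161, with or without race-by-wave terms.
- Change from baseline: variance 2(1 − 0.5) × V_T = 0.02778; SE 0.167 as written. With race-by-wave terms, 2(1 − 0.5) × V = 0.04167; SE 0.204. Ratio 1.22.
- 18-month difference: 0.02604 + (1 − 0.5)(3/4) × 0.02778 = 0.03646; SE 0.191 as written. With race-by-wave terms, √0.04167 = 0.204. Ratio 1.07.

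**False-positive rates as written.** For single contrasts, P(|Z + bias/SE| > 1.96). The joint test uses a noncentral chi-square on 4 df, with noncentrality equal to the sum of squared biases divided by (0.5 × V_T). For D = 0.3 this is 0.05/0.01389 = 3.6.

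| Drift D (SD) | 18-month bias | bias/SE | false positives | change bias | bias/SE | false positives | joint test |
|---|---|---|---|---|---|---|---|
| 0.2 | 0.10 | 0.52 | 8% | 0.20 | 1.20 | 22% | 14% |
| 0.3 | 0.15 | 0.79 | 12% | 0.30 | 1.80 | 44% | 29% |
| 0.4 | 0.20 | 1.05 | 18% | 0.40 | 2.40 | 67% | 50% |

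A generalised least squares fit at D = 0.3 gives the same biases and standard errors. With race-specific wave intercepts, the bias is 0 at every wave and the error rate is 5%. With D = 0, the model as written also has zero bias and 5% error.

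**Two other readings, both at 0.10 SD drift per wave.**
- If race is not in X, the spurious difference is 0.30 SD at 18 months and 0.15 SD averaged over waves.
- If d_l is taken literally as one multiplier per race, the pattern under no effect is the same as in the main case. With an equal true effect of 0.20 SD at 6, 12 and 18 months in both groups (50/50 split), the fit gives about 0.12 versus 0.29 SD at 18 months and a wave-averaged race difference of about 0.11 SD.

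**The case against.** The strongest reply is that the problem is conditional. No document reports any race difference in trend; the drifts of 0.2 to 0.4 SD are assumed. Without drift the model is correct, and borrowing controls across groups is a legitimate gain in precision. This stands, and it is why the sizes above are only illustrations. It does not remove the point: equal trends are an unstated assumption, and E.3 itself starts from the premise that families differ in their exposure to structural racism.

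Four stronger readings might be inferred, and the documents do not support them.
- *The whole drift turns into a false 18-month effect.* E.2 defines the effect as treated minus control. On that scale, with race in X, the 18-month bias is half the drift. The full drift appears in the change-from-baseline contrast, which the plan does not define as an estimand.
- *All race contrasts are biased.* Under free interactions with race in X, the wave-averaged difference is unbiased.
- *The standard errors are wrong.* The smaller SE is correct for the estimator that E.3 fits; the fault is bias when trends differ.
- *The primary results are at risk.* The agency outcomes in D.2 are one count or binary per family over the 18 months, with no wave trend to misattribute.

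It is also fair that the main calculation uses free interactions rather than the literal multiplier d_l. The literal form has the same omission, and with a non-zero effect it biases the wave average too.

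**Conclusion.** The point holds as a conditional specification fault in a secondary analysis. As written, E.3 cannot separate a race difference in trend common to both arms from a race difference in the wave-specific or changing effect of cash. Under the stated assumptions, a drift of 0.2 to 0.4 SD produces a spurious 18-month race difference of 0.10 to 0.20 SD (8% to 18% false positives). In the change from baseline it is 0.20 to 0.40 SD (22% to 67%), and the joint test rejects in 14% to 50%. These rates are before any multiplicity adjustment and apply to the linear model. The logit and negative binomial models omit the same term on the link scale, but their error rates were not computed. The algebra is certain; whether any drift will occur, and how large, is unknown. The change is worth making before analysis because the output concerns which racial groups benefit, and no planned sensitivity analysis would reveal the problem.

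**What to change.** In E.3, for the survey outcomes, name the race main effect explicitly and replace δ_j with race-specific wave intercepts δ_jl beside the treatment-by-race-by-wave terms. Each group's treated families are then compared with that group's own controls at each wave. State also which race contrast will be reported (each wave, change from baseline or wave average), since the exposure to bias differs between them. The agency outcomes need no such term.

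The cost is SAP wording and a few more coefficients, with no new data. Under the assumptions above, the standard error grows by about 7% for the 18-month race difference (0.191 to 0.204) and 22% for the change-from-baseline difference (0.167 to 0.204). It stays at 0.161 for the wave average.
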